6.1.8. Dose Limiting Toxicity

If 2 participants in a cohort meet individual stopping criteria, the entire cohort will be stopped or dose-reduced.

6.2. Participant Withdrawal from the Study

Participants and/or their parent or guardian are free to withdraw from the study at any time upon request. If the participant/parent/guardian withdraws consent for disclosure of future information, the

Sponsor may retain and continue to use any data collected before the withdrawal of consent. The participant's parent or guardian may request destruction of any samples taken and not tested, and the Investigator must document this in the site study records.

Participants will be withdrawn from the study by the Investigator and/or Sponsor for either of the following:

- Pregnancy
- If any clinical AE, laboratory abnormality, or other medical condition or situation occurs such that continued participation in the study would not be in the best interest of the participant

A participant may also be withdrawn from the study by the Investigator and/or Sponsor at any time for other safety, behavioral, compliance, or administrative reasons such as the following:

- Significant protocol deviation or noncompliance with study procedures/restrictions
- If the participant no longer meets eligibility criteria
- Study termination by the Sponsor

If possible, an ET visit (see Schedule of Activities in [Appendix 1](#) and [Appendix 2](#)) should be conducted for any participant that received at least one dose of study drug before participant withdrawal. The Investigator must document the date and primary reason for the withdrawal on the appropriate eCRF. Participants who withdraw prematurely may be replaced at the discretion of the Sponsor to ensure adequate numbers of evaluable participants.

6.3. Lost to Follow-up

A participant will be considered lost to follow-up if the participant fails to attend scheduled visits and study personnel are unable to reach the participant.

The following actions must be taken if a participant fails to attend a required study visit:

- The site must attempt to contact the participant and/or their parents/guardians and reschedule the missed visit as soon as possible, counsel the participant on the importance of maintaining the assigned visit schedule and ascertain whether the participant wishes to and/or should continue in the study.
- Before a participant is deemed lost to follow-up, the Investigator or designee must make every effort to regain contact with the participant and/or their parents/guardians, including, where possible, making 3 telephone calls to the participant and, if necessary, sending a certified letter to the participant's last known mailing address (or local equivalent methods). Attempts to contact the participant should be documented in the participant's medical record.
- If the participant continues to be unreachable, the participant will be considered to have withdrawn from the study with a primary reason of lost to follow-up.

7. STUDY ASSESSMENTS AND PROCEDURES

The timing of study assessments and procedures is provided in the Schedule of Activities in [Appendix 1](#) (Cohorts 1-3) and [Appendix 3](#) (Cohorts 4-9). The Schedule of Activities for the extension period is provided in [Appendix 2](#) (Cohorts 1-3) and [Appendix 4](#) (Cohorts 4-9).

7.1. Safety Assessments

Safety assessments will include monitoring and recording all AEs (including SAEs, AEs leading to discontinuation/withdrawal, DLTs, and AESIs), physical examination, vital signs assessment, ECGs, and clinical laboratories. AE procedures are described in [Section 7.2](#).

7.1.1. Physical Examination

A full physical examination should include assessments of the cardiovascular, respiratory, abdomen, neurological, and musculoskeletal systems; head, eyes, ears, neck, and throat; thyroid; skin; and extremities. The full physical examination may exclude rectal, genitourinary, and breast exams.

An abbreviated/directed physical examination should include the following components: cardiovascular, respiratory, abdomen, and any other systems indicated by history or clinical judgment.

Investigators should pay special attention to clinical signs related to previous serious illnesses.

7.1.2. Vital Signs

Vital signs consist of systolic and diastolic blood pressure, pulse rate, respiration rate, and body temperature. The participant should ideally have an empty bladder. Vital signs will be measured as specified in the Schedule of Activities ([Appendix 1](#) and [Appendix 2](#)) and as clinically indicated.

7.1.3. Body Weight and Height

Total body weight (actual body weight) will be measured at every visit using a calibrated balance. Height needs to be recorded at Screening only. Body mass index (BMI) and body surface area (BSA) will be calculated using these measurements.

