3.1.2.1. Visit 1 (Screening)

Initial Screening will be conducted as an outpatient visit at approximately Day -14; the screening window may be extended with Sponsor/Medical Monitor (MM) approval. The following activities will be performed:

- Informed consent/assent and/or parent/legal guardian permission, as applicable (prior to undergoing any study procedures)
- Assessment of participant eligibility (Inclusion/Exclusion Criteria)
- Review of demographics, medical history, and medications (both current and from the past year)
- Hepatitis B, C, and human immunodeficiency virus (HIV) screening
- Pregnancy test for females of childbearing potential (FOCP) (serum)
- Screening/safety labs (see [Appendix 1](#) and [Appendix 3](#))
- Urinalysis
- Vital signs: blood pressure, pulse rate, body temperature, respiration rate, weight, and height (height is only measured during the Screening Visit).
- Physical exam (abbreviated/directed)
- 12-lead ECG
- Baseline Suicidality Questionnaire- Columbia–Suicide Severity Rating Scale (C-SSRS) (for participants aged ≥ 6 years only)
- Baseline Depression and Anxiety Questionnaires (Patient Reported Outcomes Measurement Information System [PROMIS] (for participants aged ≥ 5 years only) or Survey of Well-being of Young Children [SWYC] depending on age of participant)
- Bone age and predicted adult height calculated from x-ray image of left hand and wrist (if deemed appropriate by the principal investigator). Alternatively, a calculation using historical data is acceptable if image is within 6 months prior to screening. An x-ray may be repeated at the discretion of the Investigator. This will not be performed in adults (Cohorts 4 & 5).

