- Physical exam (abbreviated/directed)
- Vital signs: blood pressure, pulse rate, body temperature, respiration rate, and weight
- Safety labs (see [Appendix 2](#) and [Appendix 4](#))
- Pregnancy test for FOCP (urine)
- Urinalysis (Weeks 48 and 96 only)
- Pharmacodynamics (ACTH, 17-OHP, A4, testosterone, and 11KT) drawn prior to GC dosing at approximately 8 AM (\pm 1 hour). Fasting is not required.
- Tildacerfont concentration (single sample)

SPR001-205
Spruce Biosciences, Inc.

CLINICAL STUDY PROTOCOL
Version 5.0

- Study drug accountability
- Suicidality Questionnaire- C-SSRS since last visit (participants aged ≥ 6 years only)
- Depression and Anxiety Questionnaires (PROMIS or SWYC depending on age of participant)
- GC dosing adjustments
- Assess for AEs
- Bone age and predicted adult height calculated from X-ray image of left hand and wrist (every 6 months if deemed appropriate by Investigator, see [Appendix 2](#) and [Appendix 4](#)).
- Tildacerfont dose adjustment as needed (based on recommendation of investigator or due to weight-based dosing changes)

4. STUDY POPULATION**4.1. Eligibility Criteria****4.1.1. Inclusion Criteria**

A participant must meet all of the following criteria to be eligible for this study:

1. Male and female participants aged 2- to 10-years (Cohorts 3, 7, and 9), 11- to -17 years (Cohorts 1, 1a, 2, 6, and 8), and ≥ 18 years (Cohorts 4 and 5) at Screening.
2. For participants aged 2 to 5 years, a minimum weight at Screening of 11 kg.
3. Has a known childhood diagnosis of classic CAH due to 21-hydroxylase deficiency (21-OHD) based on genetic mutation in CYP21A2 and/or documented (at any time) elevated 17-OHP and currently treated with hydrocortisone (HC), HC acetate, prednisone, prednisolone, methylprednisolone (or a combination of these). Other types of CAH may be allowed with Sponsor approval.
4. For participants in Cohorts 4-9, $1.2X \text{ ULN} < A4 < 4X \text{ ULN}$. A4 values outside of this range may be allowed with Medical Monitor (MM) approval.
5. A stable dose of GC replacement for ≥ 1 month before Screening without evidence of non-adherence (as assessed by Investigator). Weight-based dose adjustments or stress dosing in the month prior to Screening are not exclusionary but should be discussed with the MM.
6. For participants on mineralocorticoid replacement, a stable dose for ≥ 1 month prior to Screening.

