¹⁰ In all cohorts, GC dose (frequency or total daily dose) may be adjusted based on A4 levels collected at Weeks 4 and 8 (all participants) and Week 12 (for those participants continuing in the optional EP). If a change in GC is warranted by the A4 algorithm, sites will contact participants by telephone after receipt of results (within approximately 2 weeks) after each applicable study visit.

¹¹ Urinalysis should include the following: specific gravity, pH, glucose, protein, blood, ketones, bilirubin, urobilinogen, nitrite, by dipstick. Microscopic examination should be obtained if blood or protein is abnormal. For visits in which tildacerfont is administered, urinalysis should be performed pre-dose.

¹² Systolic and diastolic blood pressure, pulse rate, body temperature, and respiration rate. Height will only be collected at Screening.

¹³ Full physical exam is performed at Visit 2, Visit 6, and ET Visit; an abbreviated/directed physical exam is performed at all other visits.

¹⁴ Day 1 ECGs are conducted pre-dose. Day 14 ECG is dose independent, as participants should be at steady state.

¹⁵ Historical bone age and predicted adult height calculation may be used if performed \leq 6 months prior to Screening. If no appropriate image is available, x-ray of left hand and wrist will be performed to assess bone age and calculate predicted adult height.

¹⁶ The C-SSRS, to assess suicidality, is only conducted for participants aged 6 to 17 years.

¹⁷ PROMIS, to assess anxiety and depression, is conducted for participants aged 5 to 17 years.

¹⁸ The SWYC to assess anxiety and depression is only conducted in Cohort 3 participants \leq 5 years of age.

¹⁹ A 12-week supply of study drug will be dispensed at Visit 2 (Day 1). Participants should bring study drug to all visits for accountability. Upon receipt of study drug, the pharmacy will hold/store two doses to ensure that in-clinic dosing can occur at Visit 3 (Week 2) in the event a participant does not bring study drug to the visit.

²⁰ Cohorts 1 and 2 dosing:

Cohorts 1 and 2 (and 1a if indicated) will dose with a morning meal for the first 14 days of the study. Cohorts 1 and 2 (and 1a if indicated) will take the study drug at the clinic on Day 1 (Visit 2) (to allow for a 1-hour safety observational period and serial tildacerfont concentrations), and on Day 14 (to allow for serial tildacerfont concentrations).

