#### *5.3.1.4 Body Weight and Height*

Total body weight (actual body weight) will be measured at every visit using a calibrated balance. Height needs to be recorded at Screening and every 6 months thereafter (for those enrolled in the extension). Body mass index (BMI) and body surface area (BSA) will be calculated using the most recent of these measurements. In the extension period, height will need to be updated, as growth dictates changes in BSA and therefore GC dose. The most recent height and weight values will be used when BMI and BSA are reported during the extension period.

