### 9.4.7 *Body Surface Area*

Body surface area is calculated per the Mosteller formula as  $\text{sqrt}((\text{height} (\text{cm}) \times \text{weight} (\text{kg})) / 3600)$ , rounded to one decimal place. The most recent height measured will be used in all BSA calculations.

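### The protocol records height at Screening only while the SAP assumes six-monthly height for extension BSA; unless this is resolved, glucocorticoid dose per m² in growing children would rest on Screening height

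*Protocol*

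**What the plan says.** **Protocol v5.0.** Section 7.1.3 states "Height needs to be recorded at Screening only". Section 3.1.2.1 agrees ("height is only measured during the Screening Visit"), and so does footnote 12 of Appendices 1 and 3 ("Height will only be collected at Screening"). The extension visit list in Section 3.1.3 reads "Vital signs: blood pressure, pulse rate, body temperature, respiration rate, and weight". The extension schedules in Appendices 2 and 4 have a row for vital signs and body weight, and neither the row nor its footnote mentions height. Weight is different: "Total body weight (actual body weight) will be measured at every visit using a calibrated balance". Section 7.1.3 then says "Body mass index (BMI) and body surface area (BSA) will be calculated using these measurements".

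**SAP v2.0.** Section 5.3.1.4 states "Height needs to be recorded at Screening and every 6 months thereafter (for those enrolled in the extension", and gives the reason: growth changes BSA and, through it, GC dose. Section 5.3.1.3 repeats the six-monthly schedule. Section 9.4.7 defines BSA by the Mosteller formula, rounded to one decimal, and adds "The most recent height measured will be used in all BSA calculations". In its copies of the main-period schedules (Tables 8 and 10), footnote 12 says every six months where the protocol says Screening. The SAP's extension schedules (Tables 9 and 11) have no height row or footnote. Section 15 does not list the difference.

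**Where BSA is used in the extension.** Protocol Section 2 has a secondary endpoint on approximately physiologic GC dosing, with a cut-off of 11 per m² per day. Protocol Section 8.3.6 plans BSA-adjusted GC change at Week 12 and during the extension.

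**The concern.** Sites work from the protocol. If they do what it says, the most recent height in the extension is the Screening height, however long ago that was, while weight is current at every visit. The SAP's rule would run without error and give a BSA that is too small for any child who has grown.

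A BSA that is too small makes GC dose per m² too large. The error has the same sign in every growing child, so it does not average out. Fewer children would be counted at or below 11 per m² per day, and BSA-adjusted reductions would look smaller than they are. Cohorts hold 5 or 10 participants, so one misclassified child moves a cohort proportion by at least 1/10 to 1/5, that is 10 to 20 percentage points. A height that was not measured cannot be recovered later.

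**Working it through.** The plan states no figure to reproduce. The check compares the texts, as set out above, and then sizes the effect with the SAP's own formula.

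**Inputs from the documents**
- BSA = √(height in cm × weight in kg / 3600), SAP Section 9.4.7.
- Weight at every visit, Protocol Section 7.1.3.
- Treatment to about two years, Protocol Section 3.1.3. The last scheduled visit is Week 96, so two-year figures are slightly high.
- Cut-off 11 per m² per day. The endpoint tables print the unit as g/m²/d while Section 8.3.6 uses mg/m². Those passages need reconciling; only the number 11 is used here.

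**Assumptions, not in the documents**
- Growth of 0 to 8 cm/year.
- Height at Screening of 90 to 150 cm.

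**Formula.** With Screening height H0, current height Ht and current weight in both versions, weight cancels:

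- BSA from Screening height / true BSA = √(H0/Ht)
- Overstatement of dose per m² = √(Ht/H0) − 1

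**Results before BSA rounding**

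| H0 (cm) | Growth (cm/yr) | Ht at 2 years | Overstatement at 2 years | True 11.0 reads | Overstatement if height is 6 months old |
|---|---|---|---|---|---|
| any | 0 | H0 | 0% | 11.00 | 0% |
| 150 | 2 | 154 | 1.3% | 11.15 | 0.3% |
| 140 | 4 | 148 | 2.8% | 11.31 | 0.7% |
| 130 | 6 | 142 | 4.5% | 11.50 | 1.1% |
| 100 | 6 | 112 | 5.8% | 11.64 | 1.5% |
| 100 | 8 | 116 | 7.7% | 11.85 | 2.0% |
| 90 | 8 | 106 | 8.5% | 11.94 | 2.2% |

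Worked row: √(116/100) = 1.077, and 11.0 × 1.077 = 11.85.

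**Who changes class at the cut-off.** Only children whose true value lies between 11/√(Ht/H0) and 11: from 11/1.028 = 10.7 upward at 140 to 148 cm, and from 11/1.077 = 10.2 upward at 100 to 116 cm.

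**Effect on a reduction.** Take a true fall from 12.0 to 11.0 per m² at two years, with the baseline correct. It would display as 12.0 − 11.31 = 0.69 at 140 to 148 cm and as 12.0 − 11.85 = 0.15 at 100 to 116 cm.

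**Main period.** At the fastest assumed growth, 12 weeks adds 8 × 12/52 = 1.85 cm. From 90 cm, √(91.85/90) − 1 = 1.0%. Four weeks adds 0.62 cm, giving 0.3%.

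**Rounding.** Rounding BSA to one decimal can by itself move a value by up to 0.05/0.6 = 8.3% at BSA 0.6 and 0.05/1.0 = 5.0% at BSA 1.0, in either direction. It can hide or enlarge the height effect. With an assumed 34 kg, 130 and 138 cm give 1.108 and 1.142, both rounded to 1.1. With an assumed 20 kg, 100 and 112 cm give 0.745 and 0.789, rounded to 0.7 and 0.8, a gap of 14.3%.

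**The case against.** **Height may be collected after all.** The SAP (18 April 2024) is later than Protocol v5.0 (30 November 2023) and cites Case Report Forms v7.0 (21 January 2024), which are not among the documents. SAP Section 9.4.8 describes six-monthly Tanner staging that no protocol schedule lists, so the SAP may reflect collection beyond the protocol text. The extension appendices are silent on height; the explicit Screening-only footnotes sit on the main-period schedules. This stands. A reader might infer that extension results will certainly use outdated height, and the documents do not support that. They support only the conditional statement.

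**The SAP prevails over the protocol.** SAP Section 4 gives it precedence for planned analyses. That cannot create measurements at sites, and Protocol Section 9.10 tells investigators not to change the protocol without an amendment. This objection fails.

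**Extension analysis belongs to a separate SAP.** SAP Section 4 says so, and that plan is not available. It may handle the point, but it would still need the heights.

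**The effect is modest and partial.** This largely stands. Height enters as a square root. Adolescents who have stopped growing show no error, and up to 30 of the 55 children are aged 11 to 17. Earlier extension visits show less than the two-year figures. The endpoint is itself described as approximate. One might also read the problem as hiding GC reductions altogether. It does not: Section 8.3.6 also plans change in mg, which needs no height.

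**Conclusion.** The two documents contradict each other on height collection, and the SAP does not disclose it. If the protocol is followed as written, extension GC dose per m² in growing children is overstated, always in that direction. Before BSA rounding the size at two years is 0% to 8.5%, against at most about 2.2% when height is no more than six months old. Both figures rest on assumed growth of 0 to 8 cm/year from 90 to 150 cm. After rounding, the effect on an individual child can vanish or grow.

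The measures at risk are the proportion at or below 11 per m² per day and the BSA-adjusted GC change in the extension. Adults and the main-period results are not materially affected. This is an unresolved inconsistency with a predictable direction of error. It is not a demonstrated bias in results, because the case report forms and the extension SAP have not been seen.

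**What to change.** 1. Check whether Case Report Forms v7.0 collect height every six months in the extension. If they do, the protocol text still needs correcting.
2. Amend the protocol so that height for pediatric participants is recorded at Screening and at extension Weeks 24, 48, 72 and 96, when bone age is already scheduled. Change Sections 3.1.2.1, 3.1.3 and 7.1.3 and footnote 12 of Appendices 1 and 3, and add a height row to Appendices 2 and 4.
3. In the SAP, add the same row to Tables 9 and 11, bring Sections 5.3.1.3 and 5.3.1.4 and footnote 12 of Tables 8 and 10 into line with those visits, and record the difference in Section 15 if the protocol is not amended first.
4. Carry the most-recent-height rule into the separate extension SAP.

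The cost is a protocol amendment and one height measurement at visits already held. Heights missed before the change cannot be recovered, so the extension report should state which BSA values rest on Screening height.

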7.1.4. Electrocardiogram

A 12-lead ECG will be obtained using an ECG machine that automatically calculates the heart rate, QRS, QT, and QTc intervals, preferably using QTcF. Tracings may be repeated as needed until the Investigator feels the results are reliable. Any ECG measurement assessed by the Investigator as a clinically significant abnormality should be recorded in the AE section of the eCRF and monitored until resolution.

Refer to [Section 6.1.4](#) for QT individual treatment-stopping criteria and any additional ECGs that may be necessary.

7.1.5. Clinical Laboratories

All visits will take place in the morning so that labs can be drawn prior to the first GC dose. Participants may arrive in time to have labs drawn at 7am (8am \pm 1 hour). Fasting is not required for laboratory assessments. Clinical laboratory assessments include coagulation panel (Screening only), hematology, chemistry (including liver function tests AST, ALT, ALT, gamma-glutamyl transferase [GGT], total and direct bilirubin, and total bile acids), and thyroid panel. eGFR for Screening and throughout the trial will be calculated from blood creatinine measured as part of Screening clinical chemistry utilizing the creatinine-based Schwartz equation.

A complete list of study-required clinical laboratory tests is provided in [Appendix 6](#).

All study-required clinical laboratory tests should be conducted in accordance with the laboratory manual and will be performed by a central laboratory. If it is not feasible to draw labs in clinic, local labs may be used to monitor safety. Local A4 levels may be used for GC dose adjustment during the extension period with Sponsor's approval.

The Investigator must review the laboratory report, document the review, and record any clinically significant laboratory findings that occur during the study in the AE section of the eCRF. Laboratory reports must be filed with the source documents. Clinically significant laboratory findings are those that are not associated with the underlying disease, unless judged by the Investigator to be more severe than expected for the participant's condition.

All laboratory tests with values considered clinically significantly during the Treatment Period or within 30 days after the last dose of study drug should be reported as AEs and repeated at least weekly until the values return to normal or baseline or are no longer considered clinically significant by the Investigator or MM. If such values do not return to normal/baseline within a period of time judged reasonable by the Investigator, the etiology should be identified, and the Sponsor notified.

7.1.6. Psychiatric Evaluations

Psychiatric evaluations may be conducted at any time during the study with changes in psychiatric status or if a concern arises; questionnaires may be administered on an as-needed basis.

7.1.6.1. Columbia – Suicide Severity Rating Scale

The C-SSRS will be used during the study to monitor suicidal ideation and behavior. The C-SSRS is a Food and Drug Administration (FDA)-endorsed questionnaire administered by trained study personnel to screen for suicidality risk and ideation in patients participating in trials of CNS-active compounds. The Baseline/Screening Version of the C-SSRS, which assesses both lifetime history and history from the last 12 months, will be used at screening to determine participant eligibility. The Since Last Visit Version of the C-SSRS will be used at all subsequent visits specified.

Refer to [Section 6.1.5](#) for suicidality individual treatment-stopping criteria.

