3.1.2. Study Visits

Each participant will undergo a Screening Period of up to approximately 14 days, a 12-week (Cohorts 1 to 3) or 4-week Treatment Period (Cohorts 4 to 9), and a 30-day Safety Follow-up Period. The Screening Period may be extended as approved by the Sponsor and/or contract research organization (CRO) designee. The Schedule of Activities for the study is provided in [Appendix 1](#) and [Appendix 3](#) for Cohorts 1 to 3 and Cohorts 4 to 9, respectively. The Schedule of Activities for the extension is in [Appendix 2](#) and [Appendix 4](#), respectively.

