3.1.2.2. Visit 2 (Day 1)

Visit 2 will be conducted as an outpatient visit during which a supervised first dose of tildacerfont will be administered after completion of a morning meal. The following activities will also be performed during the visit:

- Re-confirm participant meets inclusion/exclusion criteria
- Review concomitant medications for any changes
- Pregnancy test for FOCP (urine)
- For Cohorts 1, 2, 4, 5, 6, 7, 8, and 9 (and 1a if indicated), serial blood samples will be collected at 3 timepoints: pre-dose (prior to GC dosing and tildacerfont dosing), 0.5 to 1.5 hours post-GC and tildacerfont dose, and 3 to 5 hours post-GC and tildacerfont dose. After the pre-dose sample, participants will receive a meal and take their morning GC dose and study drug. Fasting is not required. Blood samples will be used to assess tildacerfont concentrations and to compare to the PBPK model, as well as PD markers including ACTH, 17-OHP, A4, testosterone, and 11KT.
 - Note: Cohorts 1 and 2 (and 1a if indicated) will receive study drug in the mornings for the first 14 days, so they will continue to take study drug at home with a morning meal until Day 14/Visit 3.
- For Cohorts 3 only one pre-dose sample will be drawn, after which participants will receive a meal and their morning GC dose and study drug. They should be observed for approximately 1 hour after receiving study drug.
 - Note: Cohort 3 will only receive the first dose of study drug in the morning to allow clinical observation. They will switch to home dosing with an evening meal on Day 2.
- Vital signs: blood pressure, pulse rate, body temperature, respiration rate, and weight (pre-dose)
- Physical exam (full)
- Safety labs (pre-dose, see [Appendix 1](#) and [Appendix 3](#))
- Dispense study drug (12-week or 4-week supply, depending on cohort)
- Assess for AEs

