3.1.2.3. Visit 3 (Week 2; Day 14 ±3 days)

Visit 3 will be conducted as an outpatient visit. Cohorts 1, 2, 4, 5, 6, 7, 8, and 9 (and 1a if indicated) will receive study drug and morning GC dose after completion of a morning meal. Cohort 3 will have received study drug the evening prior and will not require supervised dosing or a meal. Note: Cohort 1, 2, 4, 5, 6, 7, 8 and 9 (and 1a, if indicated) participants will need to bring study drug to the visit for in-clinic dosing to collect tildacerfont concentrations. The following activities will also be performed during the visit:

- Review concomitant medications for any changes
- Pregnancy test for FOCP (urine)
- Safety labs (predose; see [Appendix 1](#) and [Appendix 3](#))
- For Cohorts 1, 2, 4, 5, 6, 7, 8, and 9 (and 1a, if indicated), serial blood samples will be collected at 3 timepoints: pre-dose (prior to GC dosing and tildacerfont dosing), 0.5 to 1.5 hours post-GC and tildacerfont dose, and 3 to 5 hours post-GC and tildacerfont dose. After the pre-dose sample, participants will receive a meal and take their morning GC dose and study drug. Fasting is not required. Blood samples will be used to assess tildacerfont concentrations and to compare to the PBPK model, as well as PD markers, including ACTH, 17-OHP, A4, testosterone, and 11KT.

- Note: Cohorts 1 and 2 (and 1a if indicated) will switch to evening dosing with a meal at home on Day 15.
- For Cohorts 3, only one pre-dose sample will be drawn, after which participants will receive their morning GC dose and tildacerfont dose. Fasting is not required. Blood samples will be used to assess tildacerfont concentrations as well as PD markers including ACTH, 17-OHP, A4, testosterone, and 11KT.
- Cortisol
- Urinalysis (pre-dose)
- Vital signs: blood pressure, pulse rate, body temperature, respiration rate, and weight (pre-dose)
- Physical exam (abbreviated/directed)
- 12-lead ECG (pre-dose)
- Suicidality Questionnaire- C-SSRS since last visit (participants aged ≥ 6 years only)
- Depression and Anxiety Questionnaires (PROMIS or SWYC depending on age of participant)
- Study drug accountability
- Assess for AEs

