9. Use of any other investigational drug (other than tildacerfont) or device within 30 days or 5 half-lives (whichever is longer) prior to Screening through the end of the study (EOS). Prior exposure to tildacerfont is allowed, but tildacerfont should be discontinued for at least 2 weeks prior to randomization. The screening window may serve as the washout period.

10. Use of the following drugs from 30 days or 5 half-lives (whichever is longer) before Screening through the EOS (see [Appendix 3](#)):

- a. Rosiglitazone, testosterone, growth hormone, or any other medication or supplement that could impact participant safety or confound interpretation of study results
- b. Moderate to strong inhibitors and/or inducers of CYP3A4
- c. Sensitive substrates or narrow-therapeutic-range substrates of CYP3A4 (except hormonal contraception containing \leq 20 mcg ethinyl estradiol)
- d. Sensitive substrates or narrow-therapeutic-range substrates of BCRP (except those that can be administered QD in the morning, separated by approximately 10 hours from evening administration of study drug).

11. Donation or receipt of blood from 90 days before Screening through the EOS; donation or receipt of platelets, white blood cells, or plasma from 30 days before Screening through the EOS.

12. Any known or anticipated swallowing difficulty or dysphagia during Screening or the duration of the study.

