6.1.5. Suicidality Stopping Criteria

Tildacerfont is a central nervous system (CNS)-active drug. Some CNS-active drugs may be associated with an increased risk of suicidal ideation in certain populations. Although tildacerfont has not been shown to be associated with an increased risk of suicidal thinking or behavior in past clinical studies, participants will be monitored for such events during this study using the C-SSRS. Any participant who exhibits Suicidal Behavior or Suicidal Ideation in their responses on the C-SSRS, will have study drug immediately discontinued and should be evaluated by a psychiatrist. This safety finding will be considered an AESI if it is not an SAE (e.g., requiring hospitalization) (see [Section 7.2.8](#)).

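### The only scheduled pre-dose C-SSRS is at Screening; adding one on Day 1 would bring the suicidality baseline up to the first dose at little cost

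*Protocol*

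**What the plan says.** Protocol 7.1.6.1 has the Baseline/Screening version of the C-SSRS, which looks back over the lifetime and the past year, completed at Screening and used for eligibility. For what follows it says "The Since Last Visit Version of the C-SSRS will be used at all subsequent visits specified". The first such visit is Week 2, where Protocol 3.1.2.3 lists "Suicidality Questionnaire- C-SSRS since last visit".

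The Day 1 list in Protocol 3.1.2.2 includes "Re-confirm participant meets inclusion/exclusion criteria", a full physical examination, safety laboratory tests, an adverse event check and the supervised first dose. It has no C-SSRS. The Day 1 cell of the C-SSRS row is blank in Protocol Appendices 1 and 3 and in SAP Tables 8 and 10. SAP 5.3.1.7 names only Weeks 2, 4, 8 and 12 after Screening.

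Screening is nominally no more than 14 days before Day 1, but Protocol 3.1.2 adds: "The Screening Period may be extended as approved by the Sponsor" (or a CRO designee). No upper limit is given.

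Protocol 6.1.5 explains why the instrument is used: "Tildacerfont is a central nervous system (CNS)-active drug". It sets the individual consequence: "Any participant who exhibits Suicidal Behavior or Suicidal Ideation in their responses on the C-SSRS, will have study drug immediately discontinued". Protocol 6.1.8 sets the cohort consequence: "If 2 participants in a cohort meet individual stopping criteria, the entire cohort will be stopped or dose-reduced".

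**The concern.** The protocol relies on the C-SSRS twice: to decide who may enter and to decide who must stop. Between those uses lies the day on which eligibility is checked again and the drug is first given, and the form is absent that day. A participant whose ideation begins after Screening could therefore be dosed without any required structured question on the subject. That participant could then take the drug for about two weeks before the next scheduled C-SSRS.

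A positive Week 2 form would also be harder to interpret. The Investigator, the Medical Monitor and the Data Monitoring Committee would want to know whether the ideation was new on drug. The most recent structured answer would be at least as old as the Screening-to-dose interval. With planned dose groups of about 5 in most of Cohorts 4-9, each case will be examined closely.

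**Working it through.** The plan gives no figure of its own here, so the check compares schedules and counts days.

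**Inputs**
- Screening to Day 1: up to 14 days (Protocol Appendices 1 and 3), extendable (3.1.2).
- Week 2 visit: Day 14 ± 3 days (3.1.2.3).
- C-SSRS from age 6 (3.1.2.1 and Appendix 3, footnote 16).
- Planned maximum for Cohorts 4-9: 15 adults, 15 aged 11-17 and 15 aged 2-10 (Protocol 3.1).

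**Visits with and without the form (main period)**

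| Cohorts | Scheduled clinic visits | C-SSRS scheduled | Missing |
|---|---|---|---|
| 1-3 | Screening, Day 1, Weeks 2, 4, 8, 12 (6) | 5 | Day 1 |
| 4-9 | Screening, Day 1, Weeks 2, 4 (4) | 3 | Day 1 |

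The visit text, all four schedule tables and SAP 5.3.1.7 agree. The blank Day 1 cell is therefore not a table-reading fault.

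**Time on drug before the next scheduled form.** Week 2 study day − 1: 14 − 1 = 13 days, with a range of 11 − 1 = 10 to 17 − 1 = 16.

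**What the Week 2 form covers.** The documents do not say whether the last visit means Day 1 (Visit 2) or the last visit at which the C-SSRS was given (Screening). With Screening 14 days before dosing:

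- *It means Day 1.* The form covers on-drug days only. None of the 14 Screening-to-dose days is covered by any C-SSRS. Ideation that began and ended in that interval goes unrecorded on the form. Ideation that began there and persisted is reported at Week 2 with no later comparison than Screening.
- *It means Screening.* Every day is covered, but pre-dose and on-drug days are mixed. Pre-dose share = 14 / (14 + Week 2 study day − 1):
  - Day 11: 14/24 = 58%
  - Day 14: 14/27 = 52%
  - Day 17: 14/30 = 47%

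The two results belong to alternative readings and must not be added together. An extended Screening makes either one worse.

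**With a Day 1 pre-dose form.** Both readings start the Week 2 recall on Day 1. It then covers 13 on-drug days (10 to 16), and the interval from the last structured assessment to first dose falls from up to 14 days, or more if extended, to 0.

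**Extra forms.** 15 + 15 + (0 to 15, depending on how many in Cohorts 7 and 9 are 6 or older) = 30 to 45.

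**The case against.** The strongest reply is that a baseline at Screening is a legitimate design choice and that other safeguards already cover the interval. Most of this is right:

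- The Screening C-SSRS is a structured pre-dose record. A reader might infer that the plan has no such record at all, and the documents do not support that.
- Adverse events are recorded from consent with start dates (7.2.3, 7.2.4). Day 1 includes an adverse event check, and 7.1.6 allows questionnaires whenever a concern arises. These may catch or date some cases. They depend on someone volunteering or suspecting the problem, and none requires a structured question before dosing.
- Protocol 6.1.5 also states that past clinical studies have not linked tildacerfont to suicidality. Calling the drug CNS-active explains the monitoring but is no evidence of a signal.
- The C-SSRS data are listed only (Protocol 8.3.7, SAP 14.5). A reader might infer that an undated onset would distort the adverse event tables. That needs an onset which neither the adverse event record nor the psychiatric evaluation under 6.1.5 can date. The documents give no ideation rate from which to size so narrow a case.
- A reader might also infer that a Day 1 form would spare a cohort from being stopped. The rules in 6.1.5 and 6.1.8 act on ideation whatever its onset, and the proposed change leaves them alone. A different outcome arises only if someone is not dosed on Day 1.

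Re-enrolled participants deserve care. Exclusion criterion 9 allows prior tildacerfont, and "The screening window may serve as the washout period", so their new Screening form may fall at the end of earlier exposure. It does not follow that they have no off-drug C-SSRS. Anyone previously in this study has a Screening form from first entry, and what other studies collected cannot be seen here.

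What stands against the plan is narrower: the Day 1 eligibility re-check omits the protocol's own suicidality instrument, and the start of the Week 2 recall is undefined.

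**Conclusion.** The point holds as a minor, inexpensive safety improvement. The gap is in how recent the baseline is: up to 14 days old at first dose, with no stated cap if Screening is extended. Day 1 is the one scheduled main-period clinic visit without the form. The effect falls on the pre-dose safety check and on the reading of individual cases. No planned statistical analysis changes.

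The coverage figures assume Screening exactly 14 days before dosing and a Week 2 visit within its window. They describe coverage and say nothing about how often ideation would occur. The benefit is mainly for Cohorts 4-9, because 30 children in Cohorts 1-3 were already included when this amendment was written (Protocol 1.2.3).

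**What to change.** For participants still to be dosed:

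1. Add to Protocol 3.1.2.2 a C-SSRS, Since Last Visit version, completed before the first dose by participants aged 6 years and over. State that any suicidal ideation or behavior since Screening is reviewed with the Medical Monitor under Exclusion Criterion 5f before dosing.
2. Mark Day 1 in the C-SSRS row of Protocol Appendix 3 and SAP Table 10. Do the same in Appendix 1 and SAP Table 8 only if anyone is still to be enrolled in Cohorts 1-3.
3. Add Day 1 to the visit list in SAP 5.3.1.7.
4. Leave Protocol 6.1.5 and 6.1.8 as they are. A participant cleared on Day 1 who reports ideation at Week 2 would still be discontinued and counted, but with a baseline taken on the day of first dose.

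The cost is about 30 to 45 short questionnaires at a visit already scheduled, plus the matching edits in both documents. As a separate clerical matter, SAP 5.3.1.7 gives the C-SSRS age range as 6 to 17, while SAP Table 10 has 6 and over. The latter is needed for adult Cohorts 4 and 5 and could be aligned at the same time.
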